3.1 Characteristics

This is a Phase II, single-center study of pembrolizumab for the treatment of relapsed or refractory multiple myeloma (RRMM) after anti-BCMA chimeric antigen receptor T-cell (CAR-T) therapy. Eligible patients will receive pembrolizumab 200 mg over 30 minutes, intravenously, every 3 weeks for up to 2 years (35 cycles) or until disease progression/dose-limiting toxicities/discontinuation. The study will utilize a Simon's two-stage design with 15 participants enrolled in stage I and 10 additional participants enrolled in stage II assuming that at least 2 or more participants achieve a treatment response after 4 cycles of therapy during stage I of the study. The primary endpoint will be overall response rate (partial response [PR] or better by International Myeloma Working Group [IMWG] criteria) after 4 cycles of therapy. A Bayesian toxicity monitoring design will be incorporated for ongoing safety analysis during the trial to pause enrollment if at any time the rate of grade 3 or higher non-hematologic adverse events exceeds 30%.

[figure not shown]

Figure 1 Trial Schema

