3.7 Duration of Follow Up

Participants will be followed for a minimum of 30 days after last treatment or removal from study, or until death, whichever occurs first. Participants removed from study for unacceptable treatment or study-related adverse event(s) will be followed until resolution or stabilization (as determined by the investigator) or until initiation of new anti-cancer therapy, whichever occurs first.

After completing the follow-up period, participants will be followed every 12 weeks (+/- 14 days) to assess for survival/anti-cancer therapy status for up to 1 year after treatment completion or discontinuation. If possible, these visits will be done via video appointment or telephone follow-up.

Long term/Survival Follow-up visits are only required for patients who have either completed 35 cycles of therapy or have discontinued treatment for reasons other than disease progression and have not yet started treatment with another anti-cancer therapy.

Participants who experienced confirmed disease progression or start a new anticancer therapy will be taken off study. Efforts will be made to contact these participants for survival follow-up by telephone every 12 weeks (\pm 14 days) to assess for survival status until death, withdrawal of consent, or the end of the trial, whichever occurs first for up to one year after treatment discontinuation.

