7.1.3 Time to Event Definitions

Progression-free survival (PFS) is defined as the duration of time from start of treatment to time of progression or death, whichever occurs first.

Overall survival (PFS) is defined as the duration of time from start of treatment to time of death.

Time-to-next treatment (TNT) is defined as the duration of time from start of treatment to start of next line therapy.

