9.3.2 Secondary Analysis (or Analysis of Secondary Endpoints)

Continuous data will be summarized using descriptive statistics such as means, medians, standard deviations, and ranges. Categorical data will be summarized using frequency counts and percentages. Graphical summaries of selected endpoints may also be presented.

Secondary Objective and Endpoints #1 - Safety and Tolerability Analysis: The safety population will consist of all participants who receive any amount of study treatment. Safety will be assessed by evaluation of AEs. The safety analyses will be performed using the safety population. Specific AEs will be counted once for each participant for calculating rates but will be presented in total in participant listings.

Secondary Objective and Endpoints #2 -Depth of Response

Point estimate and exact binomial confidence interval will be reported for the proportion of patients achieving PD (progressive disease), SD (stable disease), PR (partial response), VGPR (very good partial response), CR (complete response), and sCR (stringent complete response) for best-achieved response at any time during pembrolizumab therapy.

Secondary Objective and Endpoints #3 -Time to Event Outcomes

For overall survival (OS), participants who remain alive at the end of study follow-up will be censored at the time when they are known to be alive. For progression-free survival (PFS), participants without progression or death will be censored at the time of the last evaluable disease assessment, while participants without a disease assessment will be censored at the date of first study treatment received. OS and PFS will be summarized using the Kaplan-Meier (KM) method. The 12-months event-free probabilities, 25th percentile, median, and 75th percentile, along with their corresponding 95% confidence intervals, will be reported. Median duration of response among the responders will be reported along with 95% confidence intervals. Competing risks analysis will be performed for analyzing time to next treatment (TNT), with death as a competing event. For patients who are alive and do not receive the next line of therapy, TNT will be censored at the last study contact. Cumulative incidence function, along with 95% confidence intervals, will be reported for TNT.

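### OS censoring time is tied to treatment duration, so Kaplan-Meier OS estimates beyond 12 months are at risk of upward bias or of not being reached

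*Combined protocol and SAP*

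**What the plan says.** Section 3.1 gives treatment "every 3 weeks for up to 2 years (35 cycles) or until disease progression/dose-limiting toxicities/discontinuation", so time on treatment varies between participants and normally ends at progression.

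Section 3.7 (repeated in 6.3.5, with the one-year limit also in footnote 1 of the 6.1 calendar) sets two follow-up paths:

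- Participants who finish 35 cycles, or stop for a reason other than progression, are seen every 12 weeks "to assess for survival/anti-cancer therapy status for up to 1 year after treatment completion or discontinuation".
- Participants who progress or start new therapy go off study. For them, "Efforts will be made to contact these participants for survival follow-up by telephone every 12 weeks", until death, withdrawal of consent or the end of the trial, "whichever occurs first for up to one year after treatment discontinuation".

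In 7.1.3, OS "is defined as the duration of time from start of treatment to time of death". In 9.3.2, "participants who remain alive at the end of study follow-up will be censored at the time when they are known to be alive". The planned Kaplan-Meier summary for OS and PFS is: "The 12-months event-free probabilities, 25th percentile, median, and 75th percentile, along with their corresponding 95% confidence intervals, will be reported". Section 3.9 expects study completion 42 months after opening. Section 9.3.2 plans no adjustment or sensitivity analysis for the OS censoring.

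**The concern.** Kaplan-Meier assumes that, at each time, participants censored alive have the same future risk of death as those still followed. Here the protocol sets the censoring time from the treatment stop date. Someone who stops at month 3 is censored alive at about month 15; someone who completes 35 cycles could be followed to about month 36.

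Beyond month 12 the risk set therefore consists increasingly of participants who stayed on treatment longer. Most treatment stops are likely to be progressions, so these are probably the participants with better prognosis. Deaths among early progressors after their one-year limit go unseen, and the later part of the curve may stay too high. Even without bias, the rule removes follow-up that the 75th percentile needs.

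At stake is a descriptive secondary summary. Section 1.4 says the time-to-event results could be set against historical controls, and that is where a favourable tail could mislead.

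**Working it through.** **The plan's own figures.** The documents state no OS rate, event count or precision, so there is no OS figure to reproduce. The Simon design (stop if at most 1 of 15; reject at 6 or more of 25; 10% versus 30%) does reproduce: early stopping probability 0.549 under the null, type I error 0.0328, power 0.8017. None of these depends on OS follow-up.

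**Follow-up implied by the text.**

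- Maximum OS follow-up = time on treatment + 12 months. Early stop: 3 + 12 = 15 months. Full treatment: 35 × 3 weeks ÷ 4.345 = 24.2 months, and 24.2 + 12 = 36.2 months.
- Accrual of 25 participants at 12-15 a year (9.1.2) takes 20 to 25 months. With study end at month 42, the last participant has at most 42 − 25 = 17 months. Only those enrolled in about the first 42 − 36 = 6 months could be followed for 36 months.

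**When bias arises.** Let T be time on treatment. At time t > 12 months, a participant alive is still under follow-up only if T ≥ t − 12. Kaplan-Meier therefore uses the death hazard among those with OS ≥ t and T ≥ t − 12, where the hazard among all with OS ≥ t is wanted. The two agree if T carries no information about the hazard at t. If longer treatment goes with lower hazard, the estimate is too high. For t ≤ 12 the one-year limit removes nobody.

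**Size, large samples.** All survival inputs below are assumptions; none is in the documents. T is capped at 35 cycles and OS is censored at T + 12 months. Times are in months.

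| Assumed relation between treatment time and survival | 75th percentile, true | 75th percentile, Kaplan-Meier |
|---|---|---|
| OS unrelated to T, OS median 6 | 12.0 | 12.0 |
| OS unrelated to T, OS median 9 | 18.0 | 18.0 |
| OS unrelated to T, OS median 12 | 24.0 | 23.7 |
| OS = T + independent later survival, medians 2 + 6 | 15.4 | 15.5 |
| Same, medians 3 + 9 | 23.2 | 24.0 |
| Same, medians 3 + 12 | 29.0 | 30.0 |
| Medians 3 + 12, correlation 0.5 | 29.7 | never reached |
| 20% responders, PFS hazard ratio 0.3, low end (2.5 + 8) | 22.6 | 25.1 |
| Same, high end (3 + 14) | about 36 | never reached |

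In the last two rows the bracket gives non-responder median PFS and median post-progression survival, with no survival advantage for responders after progression. The low-end overstatement is 25.1 − 22.6 = 2.5 months. At the high end the true value lies close to the 36.2-month ceiling, so short follow-up alone accounts for part of that result. Across the responder scenarios the median is overstated by 0 to about 3 months, the upper figure when responders also have half the post-progression hazard. Twelve-month OS was unbiased in every scenario. Adding the 42-month study end with uniform 25-month accrual changed little.

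**Size, trials of 25** (independent later survival, uniform 25-month accrual, study end at month 42; the typical estimate is the median over 4,000 trials):

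| Medians | True 75th percentile | One-year limit: typical / not reached | Common study end: typical / not reached |
|---|---|---|---|
| 2 + 6 | 15.4 | 15.4 / 19% | 15.0 / 0% |
| 3 + 9 | 23.2 | 28.5 / 48% | 22.7 / 4% |
| 3 + 12 | 28.9 | not reached / 67% | 28.9 / 18% |

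**Contact dates.** A 30-day visit followed by 12-weekly contacts puts contacts at days 30 + 84 = 114, 198, 282 and 366 after treatment ends. The fourth falls at the edge of the one-year limit, so for a very early stopper the last contact could come before month 12 from first dose.

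**The case against.** The strongest reply is that the documents do not establish bias. A reader might infer from the one-year limit that the upper tail is biased upward as a matter of fact. That does not follow. It needs treatment duration to be positively related to survival, and it needs the percentile to fall after about month 12. The documents supply no OS, PFS or post-progression survival figure, and the check includes cases with no material bias and cases with a shift of only 0.1 to 1.0 month. This stands, and it is why the point is stated as a risk. Complete independence is nevertheless hard to reconcile with stopping at progression: for a participant who stops then, time on treatment is itself part of OS.

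Next, noise. With 25 participants, 24-month OS varies between trials with a standard deviation of 13 to 16 points, against a bias of about 4 to 5 points under the responder assumptions, and 24-month OS is not a planned output. The 75th percentile will often simply be not reached. This also stands, but the limit itself raises that frequency, for example from 4% to 48% in the 3 + 9 case.

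Two further readings go too far. Section 1.4 mentions comparison with historical controls only as a possibility; 9.3.2 plans none, and no decision rests on OS. Nor is 12-month OS guaranteed sound: the limit itself does not touch it, but contact after progression is best effort, and 6.7 says withdrawn participants, with progression a listed reason, are no longer followed at scheduled visits.

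**Conclusion.** The point holds as a risk. OS censoring time equals time on treatment plus about 12 months, shortened by the study end, and nothing in 9.3.2 deals with the dependence. OS estimates beyond month 12, meaning the 75th percentile and possibly the median, are exposed to upward bias or to not being reached.

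The size is conditional on inputs that the documents do not give. With 20% responders, a PFS hazard ratio of 0.3, non-responder median PFS of 2.5-3 months and median post-progression survival of 8-14 months, the 75th percentile is overstated by about 2.5 months or more, or is never reached. The effect is smaller if survival after treatment is independent of time on treatment, and nil if OS is unrelated to treatment duration or the percentile falls before month 12. ORR, the sample size and the stopping rules are unaffected. This is a cheap improvement to a secondary summary, not a threat to the trial's main conclusion.

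**What to change.** Preferred: in 3.7 and 6.3.5, and in footnote 1 of the 6.1 calendar to match, remove the one-year limit on survival status. Continue the existing 12-weekly telephone contact for all participants, including those off study after progression, to one common calendar cut-off, the planned study end. In 9.3.2, censor participants alive at that date there, and those lost earlier when last known alive. This removes the dependence on treatment duration. In the trials of 25 above, it brought the typical 75th percentile to within 0.5 months of the true value.

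The cost is a protocol amendment and more calls per surviving participant, usually a few. The most would be for the first participant enrolled if treatment stopped at month 3: 42 − 15 = 27 extra months, and 27 × 4.345 ÷ 12 is about 10 calls.

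If follow-up is not extended, state in 9.3.2 that OS is reported by Kaplan-Meier to 12 months from first dose, with any percentile reached by then. State also that later percentiles are either not reported or are labelled as subject to informative censoring. This changes analysis wording only; the downside is that no reliable OS tail is reported.

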3.8 Primary Completion

The expected primary completion date is 30 months after the study opens to accrual.

3.9 Study Completion

The expected study completion date is 42 months after the study opens to accrual.

4 Investigational Products

4.1 Description, Supply, and Storage of Investigational Products

4.1.1 Pembrolizumab

Classification

Pembrolizumab is a humanized monoclonal antibody that blocks the interaction between PD-1 and its ligands, PD-L1 and PD-L2. Pembrolizumab is an IgG4 kappa immunoglobulin with an approximate molecular weight of 149 kDa.

Mechanism of Action

Binding of the PD-1 ligands, PD-L1 and PD-L2, to the PD-1 receptor found on T cells, inhibits T cell proliferation and cytokine production. Upregulation of PD-1 ligands occurs in some tumors and signaling through this pathway can contribute to inhibition of active T-cell immune surveillance of tumors. Pembrolizumab is a monoclonal antibody that binds to the PD-1 receptor and blocks its interaction with PD-L1 and PD-L2, releasing PD-1 pathway-mediated inhibition of the immune response, including the anti-tumor immune response.

Metabolism

Pembrolizumab is catalyzed into small peptides and single amino acids via general protein degradation, but it does not rely on metabolism for clearance.

Contraindications

None.

Formulation, Appearance, Packaging, and Labeling

Pembrolizumab, manufactured by Merck, is supplied as a sterile, preservative-free, clear to slightly opalescent, colorless to slightly yellow solution that requires dilution for intravenous infusion. Each vial contains 100 mg of pembrolizumab in 4 mL of solution. Each 1 mL of solution contains 25 mg of pembrolizumab and is formulated in: L-histidine (1.55 mg), polysorbate 80 (0.2 mg), sucrose (70 mg), and Water for Injection, USP.

Supplies will be labeled in accordance with regulatory requirements.

Availability

Pembrolizumab is being obtained as commercial supply provided by Merck.

Storage and handling

Pembrolizumab is stored at the UCSF investigational pharmacy.

Clinical supplies must be stored in a secure, limited-access location under the storage conditions specified on the label. Receipt and dispensing of trial medication must be recorded by an authorized person at the trial site. Clinical supplies may not be used for any purpose other than that stated in the protocol.

Store vials under refrigeration at 2°C to 8°C (36°F to 46°F) in original carton to protect from light. Do not freeze. Do not shake.

Side Effects

Complete and updated adverse event information is available in the Investigational Drug Brochure (IB) and/or product package insert.

4.2 Accountability Records for Investigational Product

UCSF Investigational Drug Services (IDS) will manage drug accountability records for UCSF study supply of investigational product(s).

4.3 Ordering Investigational Product

UCSF will obtain pembrolizumab directly from Merck.

4.4 Returns and Reconciliation

The investigator is responsible for keeping accurate records of the clinical supplies received from Merck or designee, the amount dispensed to and returned by the participants, and the amount remaining at the conclusion of the trial.

Upon completion or termination of the study, all unused and/or partially used investigational product will be destroyed at the site per institutional policy. It is the Investigator's responsibility to arrange for disposal of all empty containers, provided that procedures for proper disposal have been established according to applicable federal, state, local and institutional guidelines and procedures, and provided that appropriate records of disposal are kept.

5 Treatment Plan

5.1 Dosage and Administration

Treatment will be administered on an outpatient basis.

Trial interventions should be administered on Day 1 of each cycle after all procedures/assessments have been completed as detailed in the Trial Flow Chart (Fig. 1, Section 3.1). Trial interventions may be administered up to 3 days before or after the scheduled Day 1 of each cycle after Cycle 1 if needed for administrative reasons.

Pembrolizumab 200 mg will be administered as 30-minute IV infusion every 3 weeks. Sites should make every effort to target infusion timing to be as close to 30 minutes as possible. However, given the variability of infusion pumps from site to site, a window of -5 minutes and +10 minutes is permitted (i.e., infusion time is 30 minutes: -5 min/+10 min).

The Pharmacy Manual contains specific instructions for the preparation of the pembrolizumab infusion fluid and administration of infusion solution.

Table 5.1 Regimen Description

Investigational Product	Premedication; precautions	Dose	Route	Schedule	Cycle Length
Pembrolizumab	N/A	200 mg	Intravenous	Day 1 of each 3-week cycle	3 weeks (21 days)

Trial intervention should begin as close as possible to the date on which intervention is allocated/assigned. The treatment is planned for a maximum of 35 cycles or until progression of disease/dose-limiting toxicities.

At least two doses of tocilizumab per patient must be available on site prior to dosing of pembrolizumab.

5.2 Dose Modifications and Dosing Delays

AEs associated with pembrolizumab exposure may represent an immunologic etiology. These immune-related AEs (irAEs) may occur shortly after the first dose or several months after the last dose of pembrolizumab treatment and may affect more than one body system simultaneously. Therefore, early recognition and initiation of treatment are critical to reducing complications. Based on existing clinical study data, most irAEs were reversible and could be managed with interruptions of pembrolizumab, administration of corticosteroids, and/or other supportive care. For suspected irAEs, ensure adequate evaluation to confirm etiology or exclude other causes. Additional procedures or tests such as bronchoscopy, endoscopy, skin biopsy may be included as part of the evaluation. Dose modification and toxicity management guidelines for irAEs associated with pembrolizumab are provided in Table 5.2-1. Additional guidelines for toxicity management for cytokine release syndrome and neurotoxicity are outlined in Sections 5.2.1 and 5.2.2 respectively.

Table 5.2-1 Dose modification and toxicity management guidelines for immune-related AEs associated with pembrolizumab

General instructions:

Severe and life-threatening irAEs should be treated with IV corticosteroids followed by oral steroids. Other immunosuppressive treatment should begin if the irAEs are not controlled by corticosteroids.

Pembrolizumab must be permanently discontinued if the irAE does not resolve or the corticosteroid dose is not ≤ 10 mg/day within 12 weeks of the last pembrolizumab treatment.

The corticosteroid taper should begin when the irAE is \leq Grade 1 and continue at least 4 weeks.

If pembrolizumab has been withheld, pembrolizumab may resume after the irAE decreased to \leq Grade 1 after corticosteroid taper.

irAEs	Toxicity grade (CTCAE V5.0)	Action with pembrolizumab	Corticosteroid and/or other therapies	Monitoring and follow-up
Pneumonitis	Grade 2	Withhold	Administer corticosteroids (initial dose of 1 – 2 mg/kg prednisone or equivalent) followed by taper Add prophylactic antibiotics for opportunistic infections	Monitor participants for signs and symptoms of pneumonitis Evaluate participants with suspected pneumonitis with radiographic imaging and initiate corticosteroid treatment
	Grade 3 or 4, or recurrent Grade 2	Permanently discontinue		
Diarrhea / Colitis	Grade 2 or 3	Withhold	Administer corticosteroids (initial dose of 1 – 2 mg/kg prednisone or equivalent) followed by taper	Monitor participants for signs and symptoms of enterocolitis (i.e., diarrhea, abdominal pain, blood, or mucus in stool with or without fever) and bowel perforation (i.e., peritoneal signs and ileus) Participants with \geq Grade 2 diarrhea suspecting colitis should consider GI consultation and performing endoscopy to rule out colitis Participants with diarrhea/colitis should be advised to drink liberal quantities of clear fluids. If sufficient oral fluid intake is not feasible, fluid and electrolytes should be substituted via IV infusion
	Grade 4 or recurrent Grade 3	Permanently discontinue		
AST or ALT elevation or Increased Bilirubin	Grade 2 ^a	Withhold	Administer corticosteroids (initial dose of 0.5 – 1 mg/kg prednisone or equivalent) followed by taper	Monitor with liver function tests (consider weekly or more frequently until liver enzyme value returned to baseline or is stable)

irAEs	Toxicity grade (CTCAE V5.0)	Action with pembrolizumab	Corticosteroid and/or other therapies	Monitoring and follow-up
	Grade 3 ^b or 4 ^c	Permanently discontinue	Administer corticosteroids (initial dose of 1 – 2 mg/kg prednisone or equivalent) followed by taper	
Type 1 diabetes mellitus (T1DM) or Hyperglycemia	New-onset T1DM or Grade 3 or 4 hyperglycemia associated with evidence of β-cell failure	Withhold ^d	Initiate insulin replacement therapy for participants with T1DM Administer anti-hyperglycemic in participants with hyperglycemia	Monitor participants for hyperglycemia or other signs and symptoms of diabetes
Hypophysitis	Grade 2	Withhold	Administer corticosteroids and initiate hormonal replacements as clinically indicated	Monitor for signs and symptoms of hypophysitis (including hypopituitarism and adrenal insufficiency)
	Grade 3 or 4	Withhold or permanently discontinue ^d		
Hyperthyroidism	Grade 2	Continue	Treat with non-selective beta-blockers (e.g., propranolol) or thioamides as appropriate	Monitor for signs and symptoms of thyroid disorders
	Grade 3 or 4	Withhold or permanently discontinue ^d		
Hypothyroidism	Grade 2, 3, or 4	Continue	Initiate thyroid replacement hormones (e.g., levothyroxine or liothyronine) per standard of care	Monitor for signs and symptoms of thyroid disorders
Nephritis and renal dysfunction: grading according to increased	Grade 2	Withhold	Administer corticosteroids (prednisone 1 – 2 mg/kg or equivalent) followed by taper	Monitor changes in renal function
	Grade 3 or 4	Permanently		

irAEs	Toxicity grade (CTCAE V5.0)	Action with pembrolizumab	Corticosteroid and/or other therapies	Monitoring and follow-up
creatinine or acute kidney injury		discontinue		
Myocarditis	Grade 1 or 2	Withhold	Based on severity of AE administer corticosteroids	Ensure adequate evaluation to confirm etiology and/or exclude other causes
	Grade 3 or 4	Permanently discontinue		
All Other immune-related AEs	Intolerable/persistent Grade 2	Withhold	Based on severity of AE administer corticosteroids	Ensure adequate evaluation to confirm etiology or exclude other causes
	Grade 3	Withhold or discontinue based on the event ^e		
	Grade 4 or recurrent Grade 3	Permanently discontinue		

^a AST/ALT: >3.0 – 5.0 x ULN if baseline normal; >3.0 – 5.0 x baseline, if baseline abnormal; bilirubin: >1.5 – 3.0 x ULN if baseline normal; >1.5 – 3.0 x baseline if baseline abnormal

^b AST/ALT: >5.0 to 20.0 x ULN, if baseline normal; >5.0 – 20.0 x baseline, if baseline abnormal; bilirubin: >3.0 – 10.0 x ULN if baseline normal; >3.0 – 10.0 x baseline if baseline abnormal

^c AST/ALT: >20.0 x ULN, if baseline normal; >20.0 x baseline, if baseline abnormal; bilirubin: >10.0 x ULN if baseline normal; >10.0 x baseline if baseline abnormal

^d The decision to withhold or permanently discontinue pembrolizumab is at the discretion of the investigator or treating physician. For participants with Grade 3 or 4 immune-related endocrinopathy where withhold of pembrolizumab is required, pembrolizumab may be resumed when AE resolves to ≤ Grade 2 and is controlled with hormonal replacement therapy or achieved metabolic control (in case of T1DM)

^e Events that require discontinuation include but are not limited to: Guillain-Barre Syndrome, encephalitis, Stevens-Johnson Syndrome, and toxic epidermal necrolysis.

Dose modification and toxicity management of infusion reactions related to pembrolizumab**Table 5.2-2 Pembrolizumab Infusion Reaction Dose modification and Treatment Guidelines**

NCI CTCAE Grade	Treatment	Premedication at Subsequent Dosing
Grade 1 Mild reaction; infusion interruption not indicated; intervention not indicated	Increase monitoring of vital signs as medically indicated until the participant is deemed medically stable in the opinion of the investigator.	None
Grade 2 Requires therapy or infusion interruption but responds promptly to symptomatic treatment (e.g., antihistamines, NSAIDs, narcotics, IV fluids); prophylactic medications indicated for ≤24 hrs.	Stop Infusion. Additional appropriate medical therapy may include but is not limited to: IV fluids Antihistamines NSAIDs Acetaminophen Narcotics Increase monitoring of vital signs as medically indicated until the participant is deemed medically stable in the opinion of the investigator. If symptoms resolve within 1 hour of stopping drug infusion, the infusion may be restarted at 50% of the original infusion rate (e.g., from 100 mL/hr to 50 mL/hr). Otherwise, dosing will be held until symptoms resolve and the participant should be premedicated for the next scheduled dose. Participants who develop Grade 2 toxicity despite adequate premedication should be permanently discontinued from further study drug intervention	Participant may be premedicated 1.5h (± 30 minutes) prior to infusion of pembrolizumab with: Diphenhydramine 50 mg po (or equivalent dose of antihistamine). Acetaminophen 500-1000 mg po (or equivalent dose of analgesic).
Grades 3 or 4 Grade 3: Prolonged (i.e., not rapidly responsive to symptomatic medication and/or brief interruption of infusion); recurrence of symptoms following initial improvement; hospitalization indicated for other clinical sequelae (e.g., renal impairment, pulmonary infiltrates) Grade 4:	Stop Infusion. Additional appropriate medical therapy may include but is not limited to: Epinephrine** IV fluids Antihistamines NSAIDs Acetaminophen Narcotics Oxygen Pressors Corticosteroids Increase monitoring of vital signs as medically indicated until the participant	No subsequent dosing

Life-threatening; pressor or ventilatory support indicated	
is deemed medically stable in the opinion of the investigator. Hospitalization may be indicated. **In cases of anaphylaxis, epinephrine should be used immediately. Participant is permanently discontinued from further study drug intervention.
	
Appropriate resuscitation equipment should be available at the bedside and a physician readily available during the period of drug administration. For further information, please refer to the Common Terminology Criteria for Adverse Events v5.0 (CTCAE) at http://ctep.cancer.gov		

